## 7.2 Serious adverse events

### 7.2.1 Definition of SAE

An SAE is defined as any adverse event (appearance of or worsening of any pre-existing undesirable sign(s), symptom(s) or medical conditions(s)), which meets any one of the following criteria:

- is fatal or life-threatening
- results in persistent or significant disability/incapacity
- constitutes a congenital anomaly/birth defect
- requires inpatient hospitalization or prolongation of existing hospitalization, unless hospitalization is for:
  - routine treatment or monitoring of the studied indication, not associated with any deterioration in condition (specify what this includes)
  - elective or pre-planned treatment for a pre-existing condition that is unrelated to the indication under study and has not worsened since the start of study drug
  - treatment on an emergency outpatient basis for an event not fulfilling any of the definitions of a SAE given above and not resulting in hospital admission
  - social reasons and respite care in the absence of any deterioration in the patient's general condition
- is medically significant, i.e. defined as an event that jeopardizes the patient or may require medical or surgical intervention to prevent one of the outcomes listed above

Life-threatening in the context of a SAE refers to a reaction in which the patient was at risk of death at the time of the reaction; it does not refer to a reaction that hypothetically might have caused death if more severe (see Annex IV, ICH-E2D Guideline).

All malignant neoplasms will be assessed as serious under "medically significant" if other seriousness criteria are not met.

Any suspected transmission via a medicinal product of an infectious agent is also considered a serious adverse reaction.

Medical and scientific judgment should be exercised in deciding whether other situations should be considered serious reactions, such as important medical events that might not be immediately life threatening or result in death or hospitalization but might jeopardize the patient or might require intervention to prevent one of the other outcomes listed above. Examples of such events are intensive treatment in an emergency room or at home for allergic bronchospasm, blood dyscrasias or convulsions that do not result in hospitalization.

### 7.2.2 SAE reporting

To ensure patient safety, every SAE, regardless of suspected causality, occurring after the patient has provided informed consent and until 30 days after the patient has stopped study participation (defined as time of last dose of study drug taken or last visit whichever is later)

must be reported to the sponsor [or designated CRO] within 24 hours of learning of its occurrence.

Any SAEs experienced after this 30 day period should only be reported to the sponsor [or designated CRO] if the investigator suspects a causal relationship to the study drug.

Recurrent episodes, complications, or progression of the initial SAE must be reported as follow-up to the original episode, regardless of when the event occurs. This report must be submitted within 24 hours of the investigator receiving the follow-up information. An SAE that is considered completely unrelated to a previously reported one should be reported separately as a new event.

Information about all SAEs is collected and recorded on the Serious Adverse Event Report Form. The investigator must assess the relationship to study drug, complete the SAE Report Form in English, and send the completed, signed form within 24 hours to the sponsor or delegated CRO. The contact information for SAE/pregnancy reporting is listed in the investigator folder provided to each site.

The original copy of the SAE Report Form and the fax confirmation sheet must be kept at the study site.

Follow-up information is sent to the same person to whom the original SAE Report Form was sent, using a new SAE Report Form stating that this is a follow-up to the previously reported SAE. The follow-up information should describe whether the event has resolved or continues, if and how it was treated, whether the blind was broken or not, and whether the patient continued or withdrew from study participation.

If the SAE is not previously documented in the IB or Package Insert (new occurrence) and is thought to be related to the study drug, the sponsor may urgently require further information from the investigator for Health Authority reporting. The sponsor may need to issue an Investigator Notification (IN) to inform all investigators involved in any study with the same drug that this SAE has been reported. Suspected Unexpected Serious Adverse Reactions (SUSARs) will be collected and reported to the competent authorities and relevant ethics committees in accordance with Directive 2001/20/EC or as per national regulatory requirements in participating countries.

### **7.3      Pregnancy reporting**

To ensure patient safety, each pregnancy in a patient on study drug must be reported to the sponsor within 24 hours of learning of its occurrence. The pregnancy should be followed up to determine outcome, including spontaneous or voluntary termination, details of the birth, and the presence or absence of any birth defects, congenital abnormalities, or maternal and/or newborn complications.

Pregnancy should be recorded on a Clinical Trial Pregnancy Form and reported by the investigator to the sponsor. Pregnancy follow-up should be recorded on the same form and should include an assessment of the possible relationship to the study drug of any pregnancy outcome. Any SAE experienced during pregnancy must be reported on the SAE Report Form.

## **8 Data review and database management**

### **8.1 Site monitoring**

Before study initiation at a site, the protocol and (e)CRFs will be reviewed with the investigators and their staff by a sponsor representative or representative of the delegated CRO at an investigator meeting or a site initiation visit. During the study, the blinded monitor will visit the site regularly to check the completeness of patient records, the accuracy of entries on the (e)CRFs, the adherence to the protocol and to Good Clinical Practice and the progress of enrollment. In order to maintain blinding of the study, an unblinded monitor will be assigned to ensure that study drug is being received, stored, dispensed and accounted for according to specifications. Key study personnel must be available to assist the monitors during monitoring visits.

The investigator must maintain source documents for each patient in the study, consisting of case and visit notes (hospital or clinic medical records) containing demographic and medical information, laboratory data, electrocardiograms, and the results of any other tests or assessments. All information on (e)CRFs must be traceable to these source documents in the patient's file. The investigator must also keep the original informed consent form signed by the patient (a signed copy is given to the patient).

The investigator must give the monitor access to all relevant source documents for monitoring to confirm their consistency with the (e)CRF entries. The sponsor's monitoring standards require full verification for the presence of informed consent, adherence to the inclusion/exclusion criteria, documentation of SAEs, and the recording of data that will be used for all primary and safety variables. Additional checks of the consistency of the source data with the (e)CRFs are performed according to the study-specific monitoring plan. No information available in source documents about the identity of the patients will be disclosed.

### **8.2 Data collection and quality control**

Designated investigator staff will enter the data required by the protocol into the Electronic Case Report Forms using fully validated software that conforms to 21 CFR Part 11 requirements. Designated investigator site staff will not be given access to the Electronic Data Capture system until they have been trained. Automatic validation programs check for data discrepancies by generating appropriate error messages and allow the data to be confirmed or corrected before transfer of the data to the CRO working on behalf of the sponsor. Monitors will review the CRFs for completeness and accuracy and instruct site personnel to make any required corrections or additions. Subsequently, the entered data are systematically checked by Data Management staff, using error messages printed from validation programs and database listings. Queries are sent to the investigational site using an electronic data query. Designated investigator site staff is required to respond to the query and confirm or correct the data. If the electronic query system is not used, a paper data query form will be faxed to the site. Site personnel will complete and sign the faxed copy and fax it back to the CRO who will make the correction to the database. The signed copy of the Data Query Form is kept at the investigator site.

The Investigator must certify with his electronic signature that the data entered into the Electronic Case Report Forms are complete and accurate. After database lock, the investigator will receive a password protected CD-ROM or paper copies of the patient data for archiving at the investigational site.

Concomitant medications entered into the database will be coded using the WHO Drug Reference List, which employs the Anatomical Therapeutic Chemical classification system. Medical history/current medical conditions and adverse events will be coded using the Medical dictionary for regulatory activities (MedDRA) terminology.

Results of laboratory samples that will be processed centrally will be sent electronically to the designated CRO while result of the ESR performed locally would be entered into the Electronic Case Report Form by the site staff. Randomization codes and data about all study drugs dispensed to the patient and all dosage changes will be tracked using an Interactive Response Technology System (IRT). The system will be supplied by a vendor(s), who will also manage the database. The database will be sent electronically to the sponsor (or a designated CRO).

At the conclusion of the study, the occurrence of any emergency code breaks will be determined after reviewing of all code break reports and unused drug supplies to the sponsor or delegated CRO. The occurrence of any protocol deviations will be determined. After these actions have been completed and the database has been declared to be complete and accurate, it will be locked and the treatment codes will be unblinded and made available for data analysis.

Each occurrence of a code break via IRT will be reported to the clinical team and monitor. The code break functionality will remain available until study shut down or upon request of the sponsor.

### **8.3 Data Monitoring Committee**

A DMC will review the safety data of the study on a regular basis in order:

- to independently assess the causality of suspected SAEs
- to ensure periodic monitoring and periodic review of patient data on suspected SAEs
- to make recommendations based on risk assessments

A charter will be established between sponsor and the DMC to outline the DMC's responsibilities and procedures.

### **8.4 Adjudication Committee**

Not required.

## **9 Data analysis**

All data will be analyzed at the end of the trial.

The data collected in Study Period 1 will be analysed to demonstrate similar efficacy and to compare safety and immunogenicity of GP2017 and US-licensed Humira® over 24 weeks of treatment with the primary endpoint being assessed using data up to week 12.

The data including Study Period 2 will be evaluated to assess long-term safety, immunogenicity and efficacy of GP2017 up to Week 48 and to investigate the effects of a switch from US-licensed Humira® to the proposed biosimilar GP2017 in patients with at least a moderate response, with respect to efficacy, safety and immunogenicity.

All data will be collected fully blinded. All analyses shall be performed after all patients have completed or were prematurely withdrawn from the study and the study CSR shall be written.

Treatment groups for analysis will include:

- Study period 1: GP2017  
US-licensed Humira®
- Study period 2: continuous GP2017  
US-licensed Humira® switched to GP2017

Summary statistics for continuous variables will include N, mean, standard deviation, minimum, median and maximum. Summary statistics for discrete variables will be presented in contingency tables and will include absolute and relative frequencies.

If not otherwise specified, p-values will be presented as two-sided p-values and two-sided confidence intervals (CI) will be displayed.

## 9.1 Analysis sets

The following analysis sets will be used in this study:

**Study Period 1 Full analysis set (SP1 FAS):** consists of all randomized subjects to whom IMP has been assigned. Following the intent-to-treat principle, subjects will be analyzed according to the treatment assigned at randomization. Subjects will be analyzed as per the actual true strata and not necessarily the assigned strata.

**Study Period 2 FAS (SP2 FAS):** The SP2 FAS set includes all SP1 FAS patients entering Study Period 2.

**Week 12 Per-protocol analysis set (W12 PPS):** consists of all subjects in the SP1 FAS who complete Week 12/Visit 8 and do not have any **major** protocol deviations regarding the evaluation of the study's primary objective.

**Study Period 1 PPS (SP1 PPS):** consists of all subjects in the SP1 FAS who complete Week 24/Visit 14 and do not have any **major** protocol deviations regarding the evaluation of the study's key secondary objective.

**Study Period 2 PPS (SP2 PPS):** consists of all subjects in the SP2 FAS who complete the full study (Week 48/Visit 16) and do not have any **major** protocol deviations with regards to any efficacy assessment.

Additional potential exclusions from the PPS analysis sets will be assessed and confirmed during the BDRMs.

**Study Period 1 Safety analysis set (SP1 SAF):** consists of all subjects who received at least one dose of IMP, whether randomized or not. Subjects will be analyzed according to the treatment received.

**Study Period 2 SAF (SP2 SAF):** The SP2 SAF set includes all SP1 SAF patients entering Study Period 2 who received at least one dose of IMP in Study Period 2.

## **9.2 Patient demographics/other baseline characteristics**

### **Demographics and baseline characteristics**

Demographics and baseline characteristics will be summarized by treatment group using frequency tables and descriptive statistics depending variable type. The analyses will be performed for all the FAS and PPS analysis sets.

### **Medical History**

Any condition entered as medical history or current medical conditions will be coded using the MedDRA dictionary. Medical history will be summarized by system organ class and preferred term for all the FAS and PPS analysis sets. Summaries for RA specific medical history will be provided in addition.

## **9.3 Treatments (study drug, rescue medication, other concomitant therapies, compliance)**

The analysis of treatment data by treatment group will be based on the SAF analysis sets.

### **Study treatment**

Study drug exposure (including patient exposure years), duration of patient observation and compliance to study drug (including number of missed injections).

### **Prior and concomitant medication**

Prior and concomitant medications will be summarized by treatment group and for all patients separately.

Prior medications are defined as medications taken and stopped prior to first dose of study treatment. Any medication given at least once between first dose of randomized study treatment and the last day of study will be considered a concomitant medication, including those medications started prior to study treatment and which continued to be taken during the study.

Medications will be presented in alphabetical order, by Anatomical Therapeutic Classification (ATC) codes and grouped by anatomical main group. Tables will show the percentage of patients receiving at least one medication of a particular ATC code and at least one medication in a particular anatomical main group.

RA specific prior treatments will be presented including the number of prior systemic and biologic therapies, as well as the reason for discontinuation.

In addition, medical procedures and significant non-drug therapies as coded by MedDRA will be summarized.

## **9.4 Analysis of the primary objective(s)**

### **9.4.1 Variable**

The primary variable is DAS28-CRP change from baseline at Week 12.

### **9.4.2 Statistical hypothesis, model, and method of analysis**

The following statistical hypotheses will be used to assess equivalence between GP2017 and US-licensed Humira® with regards to DAS28-CRP change from baseline at Week 12:

$$H_0: |GP2017 - \text{Humira}^{\circledR}| \geq 0.6 \quad \text{versus} \quad H_1: |GP2017 - \text{Humira}^{\circledR}| < 0.6$$

To address both EMA and FDA regulatory requirements for establishing therapeutic equivalence both 95% and 90% confidence intervals shall be estimated and used to assess equivalence of DAS28-CRP change from baseline at Week 12.

Therapeutic equivalence in terms of DAS28-CRP will be concluded if the 95% (as required by EMA) or 90% (as required by FDA) confidence interval for the difference in DAS28-CRP change from baseline at Week 12 between the two treatment groups is completely contained within the interval [-0.6; 0.6]. This is statistically equivalent to calculating two independent one-sided tests at a 2.5%/5% alpha level (one in each direction), of which both have to be successful.

A mixed-model repeated measures (MMRM) analysis will be performed for DAS28-CRP change from baseline as the endpoint including treatment, stratification factors, time, the interaction between time (visits) and treatment all as categorical variables, and baseline DAS28-CRP as a continuous variable.

$$DAS28CRP_{CFB} = \text{treat} + \text{strata} + \text{time} + (\text{time} * \text{treat}) + \text{baseline DAS28CRP}$$

MMRM is a standard approach to longitudinal analysis of continuous endpoints. Its roots bear into linear mixed modeling methodology and it is specified as a multivariate normal model of the longitudinal data. More specifically, this model includes a saturated visit-by-treatment structure for the mean. That is, time is considered as a factor rather than a continuous variable, and thus MMRM makes no assumption about trends over time. Traditional linear mixed models make further assumptions about the covariance of within/intra-patient observations, which can either originate from random effects or residual errors. With MMRM the covariance structure is specified only through the residual error term. The most flexible covariance matrix is unstructured, that is, all variance and covariance parameters are estimated. The actual covariance matrix to be used shall be determined within the statistical analysis plan prior to unblinding.

Mean change from baseline at Week 12, standard errors and the two-sided 95%/90% CI for the mean difference between GP2017 and US-licensed Humira® will be estimated from the model and the 95%/90% CI compared to the pre-specified equivalence margin of [-0.6; 0.6]. An effect

size of 0.6 in DAS28-CRP score is considered to be clinically meaningful for comparison of GP2017 with US-licensed Humira® in this patient population.

The primary analysis will be performed on the Week 12 Per-protocol set (W12 PPS) which is the most appropriate analysis set to use when testing for equivalence.

#### **9.4.3 Handling of missing values/censoring/discontinuations**

No imputation will be performed for missing components of the DAS28-CRP score or the computed DAS28-CRP score itself.

#### **9.4.4 Supportive analyses**

The same MMRM analysis as used for analysis of the primary endpoint will be conducted as a sensitivity analysis using the SP1 FAS.

### **9.5 Analysis of secondary objectives**

#### **9.5.1 Key secondary variable**

The key secondary variable is time-weighted averaged change from baseline in DAS28-CRP until Week 24.

##### **9.5.1.1 Statistical hypothesis, model, and method of analysis**

Time-weighted averaged change from baseline in DAS28-CRP until Week 24 (standardized AUEC approach) will be estimated from an ANCOVA

The averaged change from Week 2 and Week 24 will be estimated by a time-weighted mean across visits. The weights are derived using the standard formula from the trapezoidal rule across the visits. Mean averaged change from baseline from Week 2 to Week 24, standard errors and the two-sided 95%/90% CI for the mean difference between GP2017 & and US-licensed Humira® will be estimated from the model and the 95%/90% CI compared to the pre-specified equivalence margin of [-0.6; 0.6].

To address both EMA and FDA regulatory requirements for establishing therapeutic equivalence both 95% and 90% confidence intervals shall be estimated and used to assess equivalence of time-weighted averaged change from baseline in DAS28-CRP until Week 24. No imputation will be performed for missing components of the DAS28-CRP score or the computed AUEC value itself.

The key secondary analysis will be performed on the Study Period 1 Per-protocol set (SP1 PPS) which is the most appropriate analysis set to use when testing for equivalence.

An identical sensitivity analysis as specified above for the SP1 PPS will be carried out using the SP1 FAS.

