Data analysis	To conclude equivalence between GP2017 and US-licensed Humira® with regards to DAS28-CRP change from baseline at Week 12, both the 90% and 95% CI of the treatment difference must be completely contained within the interval [-0.6, 0.6]. Treatment estimates and 90/95%

	
CI shall be estimated using a mixed-model repeated measures (MMRM) model.
 
Time-weighted averaged change from baseline in DAS28-CRP until Week 24 (standardized AUEC approach) will be estimated using the same MMRM used to analyze the primary endpoint.

Key words	Similar efficacy, safety and immunogenicity GP2017 to US-licensed Humira® in patients with rheumatoid arthritis (RA).

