## 2.2 Secondary objectives

### Key secondary objective

#### Study period 1: baseline (randomization) - Week 24

- To demonstrate similar efficacy of GP2017 and US-licensed Humira® with respect to time-weighted averaged change from baseline in DAS28-CRP until Week 24.

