## **9.6 Sample size calculation**

The sample size for this study is based on an expected difference of zero and common SD of 1.30 for the DAS28-CRP change from baseline at Week 12 (ReAct study), an equivalence margin of 0.6 and assumed loss of 20% patients from the per-protocol analysis set. A 0.6 change in DAS28-CRP score is considered as the minimum clinically meaningful difference by EULAR criteria and is therefore used as the equivalence margin limits [0.6,-0.6].

In order to fulfil FDA regulatory requirements for establishing therapeutic equivalence (e.g. using 90% confidence interval), a sample size of 154 patients per treatment group (to maintain

[figure not shown]
overall 246 evaluable patients for the primary endpoint analysis) will have 95% power to test the equivalence between GP2017 and US-licensed Humira®.

In order to fulfil EMA regulatory requirements for establishing therapeutic equivalence (e.g. using 95% confidence interval), a sample size of 154 patients per treatment group (to maintain overall 246 evaluable patients for the primary endpoint analysis) will have 90% power to test the equivalence between GP2017 and US-licensed Humira®.

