2.4.2 Analysis of the key secondary endpoint

Time-weighted averaged change from baseline in DAS28-CRP until Week 24 (standardized AUEC approach) will be calculated and analyzed using an ANCOVA.

The averaged change from Week 2 and Week 24 will be estimated by a time-weighted mean across visits. The weights are derived using the standard formula from the trapezoidal rule across the visits. Mean averaged change from baseline from Week 2 to Week 24, standard errors and the two-sided 95%/90% CI for the mean difference between GP2017 & and US-licensed Humira® will be estimated from the model and the 95%/90% CI compared to the pre-specified equivalence margin of [-0.6; 0.6].

Both 95% and 90% confidence intervals shall be estimated and used to assess equivalence of time-weighted averaged change from baseline in DAS28-CRP until Week 24. No imputation will be performed for missing components of the DAS28-CRP score or the computed AUEC value itself.

The key secondary analysis will be performed on the Study Period 1 Per-protocol set (SP1 PPS) which is the most appropriate analysis set to use when testing for equivalence.

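### No rule makes the key secondary equivalence verdict (until Week 24) depend on the Week 12 primary, so the two verdicts together can exceed the stated one-sided error level

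*Protocol*

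**What the plan says.** **Objective.** Protocol 2.2 words the key secondary as a demonstration: "To demonstrate similar efficacy of GP2017 and US-licensed Humira® with respect to time-weighted averaged change from baseline in DAS28-CRP until Week 24". SAP Table 2-1 does the same.

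**Assessment.** Protocol 9.5.1.1 computes both intervals with the regulators' requirements for therapeutic equivalence in view. They are "used to assess equivalence of time-weighted averaged change from baseline in DAS28-CRP until Week 24" and "compared to the pre-specified equivalence margin of [-0.6; 0.6"]. SAP 2.4.2 agrees: "Both 95% and 90% confidence intervals shall be estimated and used to assess equivalence of time-weighted averaged change from baseline". SAP 4.6.1.1 repeats the comparison and gives the formula. The endpoint also has its own power section (Protocol 9.7, SAP 2.5.2).

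**Error level.** This is stated for the primary only. Protocol 9.4.2 describes "two independent one-sided tests at a 2.5%/5% alpha level (one in each direction), of which both have to be successful".

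**Primary rule.** It appears in two forms. Protocol 9.4.2 and SAP 2.4.1 use *or*: "Therapeutic equivalence in terms of DAS28-CRP will be concluded if the 95% (as required by EMA) or 90% (as required by FDA) confidence interval" lies inside the margin. The data analysis row of the Protocol summary uses *and*: "both the 90% and 95% CI of the treatment difference must be completely contained within the interval [-0.6, 0.6"].

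**What is absent.** No section states a testing order, a gatekeeper, an alpha split or any other multiplicity rule linking the two endpoints. SAP Section 3, which lists changes to the planned analyses, adds none.

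**The concern.** Two objectives of the demonstration kind are each judged against ±0.6 at the full confidence level, and nothing connects the judgements. Two things follow.

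First, each verdict has its nominal error, but the chance that at least one of them is a false declaration of equivalence can be higher than the level the plan states.

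Second, the plan has no rule for a discordant result. If Week 12 fails and the average until Week 24 passes, the report could state equivalence until Week 24 from data that overlap heavily with the failed test, and a reader would not know what weight to give it. Discordance in this direction is quite possible. In the SAP 4.6.1.1 formula the baseline change is set to zero and enters the trapezoid, so a constant difference of 0.6 at every visit averages to less than 0.6 (step 2 of the working).

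**Working it through.** **1. The plan's own figure.** Inputs from Protocol 9.6: "expected difference of zero and common SD of 1.30 for the DAS28-CRP change from baseline at Week 12", margin 0.6, 246 evaluable patients (123 per arm), 20% loss.

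- Standard error = 1.30 × √(2/123) = 0.1658, and 0.6/0.1658 = 3.619.
- 90% interval: power = 2Φ(3.619 − 1.645) − 1 = 95.2%. The plan states 95%.
- 95% interval: power = 2Φ(3.619 − 1.960) − 1 = 90.3%. The plan states 90%.
- 123/0.8 = 153.75, so 154 per arm.

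The primary calculation reproduces. The documents give no error rate for the two verdicts together, so there is none to reproduce.

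**2. Weights in the average.** SAP 4.6.1.1 at nominal days 1, 15, 29, 85 and 169 has intervals of 14, 14, 56 and 84 days, 168 in all.

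- Week 2: 14/168 = 0.083
- Week 4: 35/168 = 0.208
- Week 12: 70/168 = 0.417
- Week 24: 42/168 = 0.250

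The sum S is 161/168 = 0.958; the remaining 1/24 sits on baseline, where the change is zero. A constant difference of 0.6 therefore averages to 0.958 × 0.6 = 0.575. The sum of squared weights is Q = 0.2865.

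**3. Correlation of the two estimates.** Assumptions, not in the documents: equal SD at every visit, the same between-visit correlation ρ for every pair of visits (compound symmetry), and the same patients in both analyses. Protocol 9.7 says only that the correlation lies between 0 and 1. Then

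r = [0.417 + ρ(S − 0.417)] / √[Q + ρ(S² − Q)].

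For ρ = 0.5: 0.6875/0.7762 = 0.89.

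**4. Chance of at least one false verdict.** Put both true differences on the same margin. Each test then passes with probability α, and

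P(at least one) = 2α − P(both),

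where P(both) is the bivariate normal tail with correlation r. For ρ = 0.5 and α = 5%: 10% − 3.07% = 6.9%.

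| ρ | r | 90% interval (nominal 5%): at least one false | of which key secondary passes, primary fails | 95% interval (nominal 2.5%): at least one false | of which key secondary passes, primary fails |
|---|---|---|---|---|---|
| 0 | 0.78 | 7.6% | 2.6% | 4.0% | 1.5% |
| 0.5 | 0.89 | 6.9% | 1.9% | 3.6% | 1.1% |
| 0.8 | 0.96 | 6.2% | 1.2% | 3.2% | 0.7% |

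Protocol 9.5.1.1 describes the average as running from Week 2 to Week 24. With the weights for that span (0.045, 0.227, 0.455, 0.273) the rates at ρ = 0, 0.5 and 0.8 are 7.6%, 6.9% and 6.2% for the 90% interval, so the choice of span does not matter here.

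**5. With a gate.** If the key secondary is tested only after the primary passes at the same level, any false verdict on the margin requires the primary to pass falsely. The maximum is then 5% or 2.5%. With identical products, the chance of passing both is 89–95% (90% interval) or 80–90% (95% interval), for a key secondary SD of 0.7–1.4 and r of 0.78–0.89.

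**The case against.** Several points on the other side are sound.

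- **The plan does not license a claim after a failed primary.** A reader might infer that key secondary equivalence is to be concluded whatever happens at Week 12. No section says so. The sentence stating when therapeutic equivalence is concluded concerns Week 12 only; for the key secondary the intervals are used to assess equivalence. There is one primary objective, and the sample size rests on it alone. The documents are silent, and the defect is that silence.
- **One headline figure would mislead.** A reader might take the excess as 7–8% against 5% for the trial. That applies to the 90% interval only, and needs a low between-visit correlation. Under the 95% interval, or the Protocol summary's rule that both intervals must fit, each test runs at 2.5% and the combined rate stays below 5%.
- **The rates are for an extreme case.** A true average of exactly 0.6 with 0.6 at Week 12 needs the other visits to average (0.6 − 0.25)/0.542 = 0.65. If only Week 12 is truly non-equivalent, the false-verdict rate stays at 5% or 2.5%.
- **A slowly building difference is not an error-rate example.** Suppose true differences of 0.3, 0.45, 0.6 and 0.6 at Weeks 2, 4, 12 and 24. The average is 0.083 × 0.3 + 0.208 × 0.45 + 0.417 × 0.6 + 0.25 × 0.6 = 0.52, inside the margin. A key secondary pass would then be correct for that endpoint. The case illustrates discordance, not a false verdict.

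What remains is that the key secondary is more than descriptive: it has a demonstration objective, a margin, full-level intervals and a power section, and no rule ties it to the primary.

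**Conclusion.** The point holds as an omission. As written, the plan lets two equivalence verdicts be reached at full level with no order between them. With both true differences on the same margin, the chance of at least one false verdict is about 6–7.6% instead of 5% (90% interval) and about 3–4% instead of 2.5% (95% interval), for between-visit correlations from 0.8 down to 0. The primary test's own error is untouched, and so is the sample size.

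These figures rest on equal visit SDs, compound symmetry and common patients. The analyses in fact use different sets (W12 PPS and SP1 PPS, the second a subset of the first in SAP 2.7.2) and different models (MMRM and ANCOVA), which may lower the correlation somewhat. At r = 0.7 the rates would be 8.0% and 4.2%. Differences on opposite margins would give about 10% and 5%, but that is hardly credible when Week 12 carries 42% of the average.

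This is a modest, cheap improvement. Its main value is a rule, set in advance, for what may be said about Week 24 when Week 12 fails.

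**What to change.** Add to Protocol 9.5.1.1 and SAP 2.4.2 a fixed sequence at each confidence level: equivalence on the key secondary is concluded with the 95% (or 90%) interval only if Week 12 equivalence was concluded with the same interval; otherwise its estimate and intervals are descriptive. Carry the same condition into SAP 4.6.1.1.

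Reconcile the primary rule at the same time. The Protocol summary requires both intervals to fit, while Protocol 9.4.2 and SAP 2.4.1 allow one or the other by agency. The 90% interval lies inside the 95% interval, so the first form reduces to the 95% rule and leaves no separate gate at the 90% level.

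The change should be fixed before unblinding. It needs no alpha split and no extra patients, and it does not alter the primary analysis. The cost is that the key secondary claim is lost when the primary fails. With identical products that is at most 100% − 95.2% ≈ 5% of trials (90% interval) or 100% − 90.3% ≈ 10% (95% interval). If the sponsor already intends this order, writing it down costs nothing. The alternative is to label the key secondary descriptive outright.
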